2.4.1. Data Linkage

Data linkage offers a means of ascertaining differences in mortality and late clinical events while minimising the trial demands on participants and sites. Participants consented to data linkage beyond the 48 month duration of the study to the Australia and New Zealand Dialysis and Transplant Registry (ANZDATA) to gather information on vital status and technique survival. The ANZDATA information will establish the durability of each intervention and medium-term effects on participant survival.

Participants also consented to long term follow-up through data linkage to the Department of Human Services Medicare Benefits Schedule (MBS) and Pharmaceutical Benefits Scheme (PBS).

The analysis of linked data and long-term follow-up outcomes will be the subject of a separate Statistical Analysis Plan.

3 Statistical Principles

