4.3 Participant Follow-up and Withdrawal

All participants were asked to participate in an intervention phase that lasted from randomisation until the earliest of:

- Completion of 48 months in the trial from randomisation, or
- In-centre/ satellite haemodialysis therapy was no longer required (eg patient receives a kidney transplant, transfers to peritoneal dialysis, transfers to home haemodialysis), or
- Transfer to a dialysis unit not able to offer both study interventions, or
- Withdrawal of consent by the participant, or
- Participant death.

Participants withdrawn from the randomised treatment for any reason (either by choice or on advice from their physician) will be followed-up according to the study follow-up schedule and analysed according to the intention-to-treat principle, providing they consent to such follow-up.

The level of withdrawal (to intervention and/or follow-up), timing and reasons for withdrawal will be recorded and presented by treatment group.

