1. The intent of secondary outcome 1b is to evaluate the proportion of people with asymptomatic disease in each group. To allow each assessment to be categorised as either asymptomatic or symptomatic, we have specified a definitive mathematical range for each category, 0-8 and 9-28 respectively. The 0-8 range represents the 'asymptomatic' range which we are more accurately describing here as 'no or minor neuropathy'.

To limit the number of comparisons and risk of Type I error we will only test for differences in binary outcomes where there has been a difference detected ($p < 0.05$) in the analysis of the continuous variable, i.e. analysis of 1b will only proceed if there is a difference in a time point in 1a, and 1d proceeds if we find a difference in 1c.

2) Safety outcomes. Analyses will include:

- a) Time to access failure, defined as thrombosis or fistula requiring revision
- b) Number of discrete episodes of access failure, defined as above.
- c) Episodes of septicaemia defined as blood culture positive septic episode without defined source.

d) Mortality

e) Cardiovascular events (composite of: cardiovascular death or any of the following requiring or occurring during a hospital admission: acute myocardial infarction, cerebrovascular event, percutaneous coronary or cerebrovascular revascularisation, or surgical coronary or cerebral revascularisation)

f) Surgery for carpal tunnel syndrome

g) Parathyroidectomy surgery

h) Fractures requiring or occurring during a hospital admission

3) Durability:

Durability is defined as adherence to the intervention at each time point

4) Ranked composite endpoint combining mortality and TNS

5) Follow-up of long term events.

a) Long-term survival at 24, 36 and 48 months following the conclusion of individual's intervention period

b) Durability of the intervention at 12, 24, 36 and 48 months following the conclusion of individual's intervention period

These events will be analysed during the post-intervention cohort observation period and will be subject to a later Statistical Analysis Plan.

Exploratory analyses:

1) By components of modified TNS: Mean change in score from baseline to end of study for:

a. Clinical symptoms (sensory and motor symptoms)

b. Physical examination (pin sensitivity, strength, tendon reflexes)

c. Nerve conduction study (sural and tibial amplitudes)

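### Long-term survival and durability (outcomes 5a, 5b) are timed from each participant's own end of intervention, an informative post-randomisation date, instead of from randomisation

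*SAP*

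**What the plan says.** Section 5.1, secondary outcome 5, lists two long-term outcomes: 5a, "Long-term survival at 24, 36 and 48 months following the conclusion of individual's intervention period", and 5b, "Durability of the intervention at 12, 24, 36 and 48 months following the conclusion of individual's intervention period". Outcome 3 in the same section supplies the meaning of durability: "Durability is defined as adherence to the intervention at each time point".

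Section 4.3 says when the period ends: "All participants were asked to participate in an intervention phase that lasted from randomisation until the earliest of" five events. They include "Completion of 48 months in the trial from randomisation, or" the point at which "In-centre/ satellite haemodialysis therapy was no longer required" (transplant, peritoneal dialysis or home haemodialysis), and "Participant death". The other two are transfer to a unit that cannot offer both treatments and withdrawal of consent.

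Section 2.4.1 gives the purpose of the registry linkage: "The ANZDATA information will establish the durability of each intervention and medium-term effects on participant survival". Section 3.2 requires intention-to-treat throughout, with every randomised participant contributing, except someone who withdraws consent for participation and use of data. Sections 2.4.1 and 5.1 leave the analysis of outcome 5 to a later SAP.

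**The concern.** A randomised comparison of survival is protected when every participant's clock starts at randomisation. Here it starts at a later date that differs between participants and that treatment or prognosis may help to set. Three difficulties follow from the text alone.

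- **Unequal time since randomisation.** The same landmark falls years earlier for someone who leaves early than for someone who completes the trial.
- **Deaths on study.** Death ends the period, so survival 24 months after it is undefined. Such a participant must be either dropped, contrary to section 3.2, or counted as a failure on a clock that starts at the event itself.
- **Durability.** If the period ended by death, transplant or a change of modality, adherence 12 to 48 months later is either undefined or already settled at time zero.

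At stake is whether 5a can measure the effect on survival that section 2.4.1 says the linkage will show.

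**Working it through.** **No figure to reproduce.** The SAP gives no event rate, expected count or power for long-term survival. The check therefore compares the definitions and then illustrates their effect under assumed rates.

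**Step 1: the clock.** A completer's period ends at month 48, so 5a is assessed at 48 + 24 = 72, 48 + 36 = 84 and 48 + 48 = 96 months from randomisation. Someone transplanted at month 12, taken as an example, is assessed at 12 + 24 = 36, 12 + 36 = 48 and 12 + 48 = 60 months.

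**Step 2: set-up.** Let h be the yearly death hazard during the intervention period, h₀ the hazard afterwards, e the yearly hazard of leaving alive, and 4 years the maximum.

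- Death within the period: D = h/(h+e) × (1 − exp(−4(h+e))).
- Survival L years after conclusion, among those alive at conclusion: exp(−h₀L).
- The same with earlier deaths kept as failures: (1 − D) × exp(−h₀L).
- Survival to 8 years from randomisation: exp(−8h₀) × E[exp((h₀−h)C)], where C is the smaller of the exit time and 4 years.

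**Step 3: true benefit during the trial only.** Assumed: h₀ = 0.12, e = 0.05 in both arms, hazard ratio 0.75 on treatment (h = 0.09) and 1 afterwards.

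- D, control = 0.12/0.17 × (1 − exp(−0.68)) = 0.348. D, treatment = 0.09/0.14 × (1 − exp(−0.56)) = 0.276.
- From randomisation at 8 years: control exp(−0.96) = 38.3%. Treatment 0.3829 × [0.05/0.02 × (1 − exp(−0.08)) + exp(−0.08)] = 0.3829 × 1.1153 = 42.7%. Difference +4.4 points.

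| Survival 48 months after conclusion | Treatment | Control | Difference |
|---|---|---|---|
| Deaths on study dropped | 61.9% | 61.9% | 0 |
| Deaths on study kept as failures | 0.7243 × 0.6188 = 44.8% | 0.6517 × 0.6188 = 40.3% | +4.5 |

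Giving participants unequal underlying risk (gamma frailty, mean 1, integrated numerically):

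| Frailty variance | From randomisation, 8 years | Deaths dropped | Deaths kept |
|---|---|---|---|
| 0.5 | +3.6 | 68.6% v 69.6% (reversed) | +3.6 |
| 1.0 | +3.0 | 73.3% v 74.7% (reversed) | +3.1 |

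**Step 4: no treatment effect, different exit rates, deaths kept as failures.** Assumed: death 13% a year in both arms, exits 5% v 10% a year.

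- e = 0.05: D = 0.13/0.18 × (1 − exp(−0.72)) = 0.371. At 24 months, 0.629 × exp(−0.26) = 48.5%.
- e = 0.10: D = 0.13/0.23 × (1 − exp(−0.92)) = 0.340. At 24 months, 0.660 × exp(−0.26) = 50.9%.
- Spurious difference about 2.4 points. At 48 months it is 39.2% − 37.4% = 1.8 points. From randomisation it is zero.

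**Step 5: lower attrition.** With h₀ = 0.04 and e = 0.016, 1 − exp(−0.224) = 20% of control periods end early. With deaths dropped and no frailty, survival 48 months after conclusion is 85.2% v 85.2%, against +2.9 points at 8 years from randomisation. With frailty variance 0.5 or 1.0 the reversal is 0.2 or 0.4 points.

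**The case against.** The strongest reply is that this SAP fixes only the wording of the landmarks. It assigns outcome 5 no model, risk set or rule for deaths on study, and leaves the analysis to a later plan. Section 3.2 points to keeping everyone, and on that reading the benefit in Step 3 survives intact. The remaining distortion needs exit rates that differ by arm, which nothing in the SAP suggests. The rates in Step 3 end 49% of control periods early, whereas the only attrition figure in the SAP is the 20% allowance in section 2.3, which does not say whether it includes death. With 60 per arm, the 95% margin on a survival difference near 45% is 1.96 × √(2 × 0.45 × 0.55/60), about 18 points, far wider than any distortion shown.

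Most of this stands, and it bounds the size. It does not remove the point: the time origin and assessment months are written here, so a later plan must inherit them or change a stated outcome. Lower attrition shrinks the reversal, but dropping deaths still hides the benefit.

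Three stronger readings are tempting, and the document does not support them.

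- **That the survival question cannot be answered.** Outcome 2d covers mortality under intention-to-treat by Kaplan-Meier, log-rank and Cox methods, and linkage supplies vital status beyond 48 months.
- **That the arms are necessarily no longer compared as randomised.** This follows only if deaths on study are excluded. If they are kept, the groups stay intact and only the clock is informative.
- **That every early leaver is off the allocated treatment at time zero of 5b.** A unit that cannot offer both treatments may still offer one of them.

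**Conclusion.** The point holds as a flaw in a stated definition. The time origin of 5a and 5b is an individual post-randomisation event that may depend on treatment and prognosis, and it fits poorly with sections 3.2 and 2.4.1. That conclusion needs no assumed rates.

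Its size does. If deaths on study are dropped, an in-trial benefit is erased, or reversed by about 1.0 to 1.4 points with frailty in the main scenario. If they are kept, the scenarios with equal exit rates show almost no distortion, and exits of 5% v 10% a year produce about 2.4 points at 24 months. All death, exit and frailty values are assumptions. The share of participants whose period ended early, which drives the harm, is not given; completers do share a fixed origin at 48 months.

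Severity is moderate to low. The outcome is secondary and deferred, and the primary analysis and 2d are untouched.

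**What to change.** - Define 5a as survival from randomisation in all randomised participants, subject to the consent exception in section 3.2, at fixed times such as 72, 84 and 96 months, counting deaths on study as deaths.
- Time 5b from randomisation too, and state how death, transplant, change of modality and transfer are counted.
- Keep survival after the end of the intervention period, if wanted, as description only.
- State in section 2.4.1 that the later SAP uses these definitions.

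The cost within this SAP is wording, since participants consented to linkage for vital status and technique survival beyond 48 months. Early leavers need linkage out to the same time since randomisation as completers. The protocol is not at hand; if it defines these outcomes in the same way, it must be aligned.

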3.1 Confidence intervals and p values

All tests are two-sided and the nominal level of alpha will be 5%. P-values will not be adjusted for multiplicity.

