5.1 Outcome Definitions

Primary Outcome

The primary end-point for this study is the difference in the mean change in modified total neuropathy score (TNS) from baseline between the two groups.

Mean changes from baseline will be analysed using a restricted maximum likelihood (REML)-based repeated measures approach (MRMM). Analyses will include the fixed, categorical effects of treatment, visit (unstructured), and treatment-by-visit interaction, as well as the continuous, fixed covariates of baseline score and baseline score-by-visit interaction. We will test a range of covariance structures (autoregressive(1), heterogeneous autoregressive(1), unstructured, compound symmetry structure) and select the structure with

the lowest AIC (best fit). The Kenward-Roger approximation will be used to estimate denominator degrees of freedom. Analyses will be implemented using SAS/Stat 14.2.

The primary comparison will be the average of the contrast between treatment groups across all time points in the study, with each observed time-point weighted equally.

Secondary Outcomes

These will follow the same plan approach for the primary outcome (MRMM), with different comparisons and distributions for the outcomes as appropriate.

1) Neuropathy outcomes. Analyses will include:

- a) Difference between groups in mean change from baseline in modified TNS at years 1, 2, 3, 4 with the same method as the primary analysis
- b) Difference between treatment groups in proportion of participants with modified TNS 0-8 (no or minor neuropathy) overall (time-points weighted equally) and at 1, 2, 3 and 4 years, using a generalised linear mixed model with a binomial distribution and a logit link.¹
- c) Difference between groups in mean change from baseline in NSS overall (as per main outcome), and at 1, 2, 3 and 4 years with the same method as the primary analysis.
- d) Difference between treatment groups in proportion of participants with no or asymptomatic neuropathy on NSS (NSS stage 0-1) overall, and at 1, 2, 3 and 4 years using a generalised linear mixed model with a binomial distribution and a logit link .
- e) Difference between treatment groups in change in sural nerve sensory amplitude (mV) from baseline overall, and at 1, 2, 3 and 4 years with the same method as the primary analysis.

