2) Quality of life measures were collected at baseline and during the follow-up period. The analysis of quality of life measures will be part of a later Statistical Analysis Plan.

3) Repeat primary and appropriate secondary analyses using original (not modified) Total Neuropathy Score.

Inter-rater reproducibility of TNS:

Neuropathy assessments were undertaken by qualified neurologists and neurophysiologists and supervised by [name], who performed the measurements in the vanguard phase of the trial. Assessors were blinded to participant treatment allocation. [name] duplicated neuropathy assessments for 5 patients to allow assessment of inter-rater reliability. Inter-rater reliability will be estimated using the Spearman's rank correlation coefficient with a 95% CI as was performed by Cornblath et al in the original description of TNS[10].

Neuropathy assessment

Neuropathy will be assessed in all participants using two validated scoring systems that incorporate clinical symptoms, examination findings and results of nerve conduction studies:

(1) Modified Total Neuropathy Score (TNS), a validated measure of peripheral nerve function[10]. (Appendix 1)

(2) Neuropathy Symptom Score (NSS) which, in conjunction with nerve conduction findings, will be used to calculate a neuropathy stage[8, 11]. (Appendix 1)

The neuropathy scores will be obtained at baseline, annually and, where possible, at anticipated transfer to another modality of renal replacement therapy (transplant, peritoneal dialysis or home haemodialysis) or transfer to a non-study centre that cannot offer both interventions, by treatment group.

Intervention: Dialysis Treatment

The adherence to the treatment allocation (haemodiafiltration versus standard high flux) at each time point will be reported and analysed.

Achieved dialysis parameters will be reported in each allocation group, including:

- Blood flow rates and dialysate flow rates
- Convection volumes (for participants randomized to haemodiafiltration)
- Pre-dialysis systolic and diastolic blood pressure
- Dialysis prescription: number of hours/session, number of sessions/week, number of hours/week
- Dialysis site: in-centre/ hospital or satellite
- Dialysis access: native AV fistula, synthetic graft, tunnelled catheter, non-tunnelled catheter, other
- Dialysate composition: Sodium, Potassium, Calcium, Glucose, addition of phosphate

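### Inter-rater reliability of the TNS rests only on a Spearman correlation from 5 duplicated assessments, which cannot show a systematic difference between raters and will be very imprecise

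*SAP*

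**What the plan says.** Under Inter-rater reproducibility of TNS, SAP section 5.1 states: "Neuropathy assessments were undertaken by qualified neurologists and neurophysiologists". They were supervised by a person who had made the measurements in the vanguard phase, and "Assessors were blinded to participant treatment allocation". The data for the reliability check are the duplicates: an assessor "duplicated neuropathy assessments for 5 patients to allow assessment of inter-rater reliability". The analysis is one sentence: "Inter-rater reliability will be estimated using the Spearman's rank correlation coefficient with a 95% CI". The reason given is that the original description of the instrument did the same.

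The SAP plans no mean rater difference, limits of agreement, ICC or weighted kappa. It names no method for the interval and gives no reason for 5 patients. It sets no threshold for acceptable reliability.

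The score concerned is the primary outcome, defined in the same section as "the difference in the mean change in modified total neuropathy score (TNS) from baseline between the two groups". The same score, cut into 0-8 and 9-28, also defines the randomisation strata (section 2.2), secondary outcome 1b (section 5.1) and the first subgroup (section 5.2).

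**The concern.** Two features of the check limit what it can show.

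First, a rank correlation answers a different question from the one a reader will bring to it. The TNS enters the analysis as a number of points and as a category with a fixed boundary, so what matters is whether two assessors would give the same patient the same score. A rater who scores everyone a few points higher ranks patients perfectly and obtains the best possible Spearman coefficient.

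Second, five pairs carry little information about any reliability coefficient, and the usual interval can fail at this size.

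At stake is what the trial can say about the quality of its primary measurement. A coefficient near 1 from this plan would be compatible both with close agreement and with a sizeable systematic difference between raters, and the report would contain nothing to tell them apart.

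**Working it through.** **Inputs.** From the SAP: 5 duplicated patients, Spearman, 95% CI (section 5.1); modified TNS range 0-28 and cut at 8/9 (section 2.2). Assumed, because the SAP gives none: observed coefficients of 0.8, 0.9 and 1.0, the method for the interval, and five illustrative scores. The SAP states no precision target for this check, so there is no planned figure to reproduce.

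**1. Response to an offset.** Take illustrative scores 2, 6, 9, 14, 20 from one rater, and let a second rater score every patient 4 points higher: 6, 10, 13, 18, 24.

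- Spearman: the ranks are 1 to 5 for both raters, so rho = 1.00.
- Two-way absolute-agreement ICC for a single rating: the sum of squares of the first rater's scores about their mean of 10.2 is 196.8. The between-patient mean square is 2 × 196.8 / 4 = 98.4, the residual is 0, and the between-rater mean square is 5 × (2² + 2²) = 40. ICC = 98.4 / (98.4 + 2 × 40 / 5) = 98.4 / 114.4 = 0.86.
- With an 8-point offset, rho is still 1.00. The between-rater mean square is 5 × (4² + 4²) = 160, and ICC = 98.4 / (98.4 + 64) = 0.61.
- With the 4-point offset, the patient scored 6 by one rater and 10 by the other moves from the 0-8 category to 9-28. Rho does not register this.

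**2. Width of the interval at n = 5.** The Fisher-z interval is tanh(atanh(r) ± 1.96 × SE), with SE = 1/√(n − 3) = 1/√2 = 0.707. The rank-variance (Bonett-Wright) correction uses SE = √((1 + r²/2)/(n − 3)).

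| Assumed rho | Method | Calculation | 95% CI | Share of −1 to 1 |
|---|---|---|---|---|
| 0.9 | Fisher z | tanh(1.472 ± 1.386) | 0.09 to 0.99 | about 45% |
| 0.9 | rank-variance | SE = √(1.405/2) = 0.838; tanh(1.472 ± 1.643) | −0.17 to 1.00 | about 58% |
| 0.8 | Fisher z | tanh(1.099 ± 1.386) | −0.28 to 0.99 | about 63% |
| 1.0 | Fisher z | atanh(1) is infinite | undefined | – |

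The undefined case is not remote. In a simulation of five bivariate normal pairs with a true correlation of 0.90, 24% of samples gave a Spearman coefficient of exactly 1.00. The exact permutation distribution over the 120 orderings tells the same story: the two-sided p is 10/120 = 0.083 at rho = 0.9 and 2/120 = 0.017 at rho = 1.0, so only perfect ranking falls below 0.05.

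**3. Precision of the alternative.** For the mean between-rater difference, the 95% half-width is t(0.975, 4 df) × SD/√5 = 2.776/2.236 × SD = 1.24 SD of the differences. If that SD were 1, 2 or 3 points (assumed), the half-width would be about 1.2, 2.5 or 3.7 points. This is imprecise too, but it is in TNS points and it targets the offset.

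**4. Effect on the treatment contrast.** Suppose follow-up scores from a second rater are shifted by d points. In the raw change score, the expected shift in the difference between arms is d × (p1 − p0), where p1 and p0 are the proportions of assessments shifted in each arm. With 1:1 randomisation and assessors blinded to allocation, there is no reason to expect p1 and p0 to differ, so the expected shift is zero. What remains is extra variance if raters differ between visits.

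**The case against.** The best defence is that this is a small descriptive check. The SAP undertakes to estimate reliability, not to pass or fail it. It attaches a 95% CI, which will itself display the imprecision, and it follows the original report of the instrument so that the two can be compared. The duplicates were already done when the SAP was written, so their number was fixed. The result feeds no model and gates no analysis. All of this stands, and it is why the point is minor. Comparability is a reason to keep Spearman, but precedent does not turn a rank correlation into a measure of agreement.

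Several stronger readings are tempting and are not supported.

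- *An offset threatens the treatment effect.* A reader might set a 4-point rater offset beside the 4.5-point difference for which section 2.3 gives 80% power. The second is a difference between arm means. A rater offset would become one only if the mix of raters differed greatly by arm, and blinding and randomisation argue against that.
- *Patients are known to have changed rater between visits.* The SAP does not say how many assessors there were, who assessed which visit, or whether vanguard patients changed assessor. Rater switching is a plausible inference only.
- *The SAP will claim established reliability.* It makes no such claim.
- *The interval covers almost the whole range.* At the assumed coefficients it covers about 45% to 63%. Very wide is accurate; almost everything is not.

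The replacement also has limits. The mean difference from five pairs is imprecise, and the usual two-way ICC presumes that the same raters scored every patient, which the SAP does not state.

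**Conclusion.** The point holds as a minor weakness in how measurement quality will be reported. The only planned statistic is unchanged by any constant rater difference: it stays at 1.00 under offsets of 4 and 8 points on illustrative scores, where absolute-agreement ICC falls to 0.86 and 0.61. Its interval is very wide at the coefficients assumed (0.09 to 0.99 or −0.17 to 1.00 at 0.9; −0.28 to 0.99 at 0.8) and cannot be computed by Fisher z at 1.0.

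What changes is what the trial can conclude about the TNS as measured here, not the primary or secondary comparisons. Any effect of a rater offset on those would mainly be added noise, and only if raters differed between visits, which is not documented. The conclusion about Spearman and offsets needs no assumption. The sizes rest on the assumed coefficients, interval methods and example scores.

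**What to change.** Keep the same five pairs and revise the analysis sentence in section 5.1 as follows.

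1. List the five pairs of TNS scores, with a code for the trial assessor in each pair. Opposite offsets from different assessors can cancel in a mean, and the list would show it.
2. Report the mean between-rater difference (duplicating assessor minus trial assessor) with a t-based 95% CI as the main agreement measure.
3. Add an absolute-agreement ICC with its CI only if the rater pairing is known, in the form that matches it: two-way if one pair of raters scored all five patients, one-way if the raters varied from patient to patient.
4. Keep Spearman as a descriptive figure for comparison with the original TNS report. Name the interval method, and say what will be reported if the coefficient is exactly 1.
5. State that five pairs cannot establish reliability.

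The cost is a few lines of SAP text and one small table. No new assessments are needed and no other analysis changes. The drawback is that the added estimates will also be imprecise, and the report should say so.
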